Withdrawal criteria and trial participant retention	Percentage or number of lost to follow-up participants	Percentage or number of participants who are lost to follow-up (i.e., have not continued in the trial until the last planned safety assessment and have not revoked consent nor have been reached by investigator site personnel through normal communication methods). These participants have not completed the trial and their status is unknown	A high number of participants lost to follow-up may indicate excessive participant burden and could impact the collection and interpretation of long-term safety and efficacy data.	10%
Procedures supporting study endpoints and data integrity	Percentage or number of study participants for whom study endpoint data was not collected	Percentage or number of study participants for whom study endpoint data was not collected; this could include	A high number of study participants for whom the failure to collect study endpoint data could impact analysis and interpretation of	15%

		inability to perform study procedure at the protocol-defined time point	study results	
Procedures supporting trial endpoints and data integrity	Percentage or number of participants with "Major" protocol deviations other than eligibility	Percentage or number of participants with protocol deviations during the trial which are not related to protocol inclusion/exclusion criteria (i.e., informed consent, trial intervention, prohibited concomitant medication, trial procedures, safety reporting, and discontinuation)	A high number of study participants with important protocol deviations during the trial could have a significant impact on interpretation of the primary endpoint and overall validity of the trial results. It can also impact participant safety	10%
Procedures supporting trial endpoints and data integrity	Percentage of participants censored in the statistical analysis because they had no bills the	Percentage or number of participants who are at risk of censoring for hospital costs	High number of participants censored for primary objective analysis would translate into smaller than assumed sample	10%

	entire time		size and may impact the interpretation of the efficacy results. Alternatively, final primary objective analysis would be delayed if required sample maturity is not reached within the assumed timelines	

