9.1 Analysis Sets

- The analysis will include the following datasets:

- Intent-to-Treat (ITT) set: Including all randomized survivors, regardless of their adherence with the entry criteria. This set will be used for the primary analysis of healthcare expenditure reduction and cancer progression.
- Per-Protocol (PP) set: Including participants who completed the trial according to the protocol without significant deviations. PP set is a subset of ITT set, excluding survivors with major protocol deviations or those who do not complete the trial. This set will be used to summarize efficacy and support sensitivity analyses.

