9.2 Analyses Supporting Primary Objective(s)

- The primary analysis will focus on quantifying the impact on total healthcare expenditure including hospitalization costs, medication expenses, outpatient visits, and any other related healthcare services over the trial period.
- We will try to establish the efficacy of Complement Theory by measuring the difference in mean total healthcare expenditure between the intervention and control groups at 3, 6, and 12 months and 18 months from baseline.
- **Statistical Model, Hypothesis, and Method of Analysis**
 - Primary Estimand (Healthcare Expenditure Reduction):
 - Null Hypothesis (H0): There is no difference in healthcare expenditure between participants in the Complement Theory program and those in the control group.
 - Alternative Hypothesis (H1): Participants in the Complement Theory program exhibit a significant reduction in healthcare expenditure compared to the control group.
 - Baseline Data Analysis: Baseline demographics and characteristics will be provided and summarized in both treatment and control groups. Standardized mean differences (SMDs) will be calculated as the measure of distance between groups. SMDs of 0.2 to <0.5, 0.5 to <0.8 and ≥ 0.8 are considered small, medium, and large, respectively. Frequencies and percentage will be provided for the binary variables as well as the

categorical variables (Yes/No); mean (standard deviation) and median (range) will be computed for continuous variables.

- Method of Analysis: A Generalized Linear Model (GLM) with an appropriate link function and distribution family that best fits the distribution of healthcare expenditure data. Both univariate and multivariate analyses will be conducted. The method will capture the effect on the outcome in treatment and control group from each independent variable. In addition, the strength of the effect from each of the variables would be evaluated through the statistical test significance, i.e., P value, at 95% confidence interval.
- **Handling of Intercurrent Events of Primary Estimand(s)**
 - For participants who discontinue the intervention or are non-adherent, we will employ a treatment policy strategy. This means all data collected will be analyzed as per the initial treatment assignment, regardless of the discontinuation or level of adherence, preserving the intention-to-treat principle.
- **Handling of Missing Data**

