9.7 Sample Size Determination

- The metric-wise sample size calculation is provided in the table below on alpha as 0.05 and power of 80% for the one-tail test at enrollment ratio = 1.

- While we are conducting the power analysis and sample size calculation based on several variables (outcomes) of interest, the sample size was computed separately for each parameter in the study and the greatest is used to obtain sample size.
- The analysis (detailed below in table) showed that sample of size of 102 is powerful enough for the analysis to cover 100% of primary and secondary metrics.
- Now since we believe that the long follow-up duration of 12 months for our trial will lead to around 30% drop-offs, we decided a final sample size of 146 (73 control, 73 test).
- So even if get 30% or 44 participants drop off we end up with final sample set of 102 (51 control, 51 test) and would be able to come to statistically significant effects ($p < 0.05$) with respect to 100% of primary and secondary metrics.

Metric Segment	Sub Metric	Control Data	Test Data	Assumed Variance	Sample Size
Primary Outcome / Concerns					
Medical Expenditure	Total Healthcare Expenditure (Planned + Unplanned)	10000	8000	Variance of 4000	102 (51 Control, 51 Test)
	No of Urgent Care Visits	3	2.5	Variance of 0.5	28 (14 Control, 14 Test)
	No of ED Visits	5	3.45	Variance of 0.8	10 (5 Control, 5 Test)
	No of unplanned outpatient/office	4.28	3.5	Variance of 0.8	28 (14 Control, 14 Test)

	visits (other than ED)				
	Unplanned Hospitalisations	5	4	Variance of 0.8	18 (9 Control, 9 Test)
	Length of hospital stay	3	2	Variance of 0.8	18 (9 Control, 9 Test)
	No of planned outpatient visits	2	1.8	Variance of 0.3	58 (29 Control, 29 Test)
	No of planned hospital visits	1.25	1	Variance of 0.1	10 (5 Control, 5 Test)
	Length of hospital stay	3	2	Variance of 0.8	18 (9 Control, 9 Test)
	Total Prescription Medicine Expenditure	1000	950	Variance of 80	80 (40 Control, 40 Test)
Secondary Outcome / Concerns					
Adherence	MMAS scale	4.5	7	Variance of 2.5	28 (14 Control, 14 Test)
QoLS Score, Pain Levels, Sleep Quality, Physical Activity	QoLS Score (FACT-G)	70	85	Variance of 20	42 (21 Control, 21 Test)
	Brief Pain Inventory (Short Form)	80	60	Variance of 35	78 (39 Control, 39 Test)

	PROMIS (Short Form)	70	55	20	46 (23 Control, 23 Test)
	GLTEQ	25	17	10	42 (21 Control, 21 Test)
	Calorie Burnt	120	198	Variance of 70	22 (11 Control, 11 Test)
Presenteeism	Attitude towards work	2	4	Variance of 1.5	16 (8 Control, 8 Test)

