Withdrawal criteria and trial participant retention	Percentage or number of lost to follow-up participants	Percentage or number of participants who are lost to follow-up (i.e., have not continued in the trial until the last planned safety assessment and have not revoked consent nor have been reached by investigator site personnel through normal	A high number of participants lost to follow-up may indicate excessive participant burden and could impact the collection and interpretation of long-term safety and efficacy data.	10%

		communication methods). These participants have not completed the trial and their status is unknown		
Procedures supporting study endpoints and data integrity	Percentage or number of study participants for whom study endpoint data was not collected	Percentage or number of study participants for whom study endpoint data was not collected; this could include inability to perform study procedure at the protocol-defined time point	A high number of study participants for whom the failure to collect study endpoint data could impact analysis and interpretation of study results	15%
Procedures supporting trial endpoints and data integrity	Percentage or number of participants with "Major" protocol deviations other than eligibility	Percentage or number of participants with protocol deviations during the trial which are not related to protocol inclusion/exclusion criteria (i.e., informed consent, trial intervention,	A high number of study participants with important protocol deviations during the trial could have a significant impact on interpretation of the primary endpoint and overall validity of the trial results. It	10%

		prohibited concomitant medication, trial procedures, safety reporting, and discontinuation)	can also impact participant safety	
Procedures supporting trial endpoints and data integrity	Percentage of participants censored in the statistical analysis because they had no bills the entire time	Percentage or number of participants who are at risk of censoring for hospital costs	High number of participants censored for primary objective analysis would translate into smaller than assumed sample size and may impact the interpretation of the efficacy results. Alternatively, final primary objective analysis would be delayed if required sample maturity is not reached within the assumed timelines	10%

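### Section 11.1 refers to censoring participants with no bills, which conflicts with the ITT comparison of mean expenditure, and Section 9 has no rule separating a confirmed zero from claims never supplied

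*Combined protocol and SAP*

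**What the plan says.** Combined protocol and SAP:

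- **Section 11.1** has a quality tolerance row for the "Percentage of participants censored in the statistical analysis because they had no bills the entire time". Its definition column reads "Percentage or number of participants who are at risk of censoring for hospital costs". Its justification column says that many participants censored from the primary objective analysis would leave fewer than the sample size assumed. The threshold is 10% and is not given by arm.
- **Section 9.1** defines the ITT set, used for the primary expenditure analysis, as "Including all randomized survivors, regardless of their adherence with the entry criteria".
- **Section 9.2** sets the primary comparison as "measuring the difference in mean total healthcare expenditure between the intervention and control groups" at 3, 6, 12 and 18 months. The model is a GLM with family and link left open. The primary analysis uses complete cases, followed by several imputation methods. Section 9 mentions neither censoring nor zero costs.

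The Protocol repeats the row in its own Section 11.1 ("participants censored in the statistical analysis because they had no bills") and still ties it to the primary objective analysis. In that document FACT-G is primary and expenditure is exploratory.

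**The concern.** Having no bills is a result, not a loss of follow-up. If a participant's claims cover the whole window and show nothing, total expenditure is fully observed and equals zero. Taking that person out compares mean cost among participants who had bills. That is neither the difference in mean total expenditure that Section 9.2 asks for nor a comparison of everyone randomized.

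The programme is meant to reduce hospitalizations, urgent care visits and outpatient visits, so the share with no bills could itself differ by arm. A saving that arises because more participants need no care would be removed from the estimate. A higher no-bill share in the control arm would inflate it. In the Combined document this affects the primary result.

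**Working it through.** **1. Inputs (Combined protocol and SAP, Section 9.7).** Mean total expenditure is 10,000 on control and 8,000 on test. The spread is listed as "Variance of 4000". The design is stated as "alpha as 0.05 and power of 80% for the one-tail test at enrollment ratio = 1". The result is 102 participants (51 per arm), raised to 146 for 30% drop-out.

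**2. Reproducing the plan's figure.** Read 4,000 as a standard deviation, so the standardized difference is 2,000/4,000 = 0.5. A one-sided two-sample t-test at 0.05 with 80% power needs 50.15 per arm, hence 51 per arm and 102 in total. Then 102/0.70 = 145.7, hence 146. Both figures reproduce. A literal variance of 4,000 would give 1 per arm, so SD 4,000 is used below.

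**3. Effect of removing zeros.** With a no-bill share p, the all-randomized mean equals (1 − p) × the mean among those with bills. Dropping the zeros therefore compares 10,000/(1 − pC) with 8,000/(1 − pT). The documents give no values for pC or pT, so the shares below are assumptions.

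| No-bill share, control/test | Pooled | Control | Test | Saving | Against 2,000 |
|---|---|---|---|---|---|
| 5%/10% | 7.5% | 10,526 | 8,889 | 1,637 | 18% lost |
| 5%/15% | 10% | 10,526 | 9,412 | about 1,115 | 44% lost |
| 10%/10% | 10% | 11,111 | 8,889 | 2,222 | 11% too large |
| 12%/8% | 10% | 11,364 | 8,696 | 2,668 | 33% too large |

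The bias cancels only when pT/(1 − pT) = 1.25 × pC/(1 − pC). Equal shares inflate the saving by 1/(1 − p).

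**4. Are these shares compatible with SD 4,000?** Zeros alone force an SD of at least mean × √(p/(1 − p)).

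- Control, mean 10,000: 5% gives 2,294; 10% gives 3,333; 12% gives 3,693.
- Test, mean 8,000: 8% gives 2,359; 10% gives 2,667; 15% gives 3,361.

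All are below 4,000, so every row of the table is feasible under the plan's own spread.

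**5. The 10% limit.** Every row has a pooled share at or under 10%. A limit not stated by arm would not detect the imbalance in rows two and four, nor the bias from equal shares in row three.

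**6. The consequence the row itself names.** Losing 10% of 102 leaves about 46 per arm. At the planned difference and SD, t-test power falls from 80.6% to 76.9%. The row guards against this modest loss of power but does not mention the bias.

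**The case against.** **The row is a monitoring entry.** Section 11.1 sets triggers for quality assurance, reviewed monthly. Section 9 specifies the analysis, and there the ITT set is everyone randomized. This stands in part. A reader might infer that the SAP prescribes deletion of no-bill participants as its analysis rule; the documents do not support that. They contain a conflict, and Section 9 does not settle it. It has no rule for zeros, and an open GLM family could be filled with a gamma, which does not admit them.

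**No bills may mean no records.** Participants supply their own claims (Sections 8 and 11.2), and access is recommended for as little as 6 months and at most 18. Some no-bill cases may therefore be missing data. This stands, and it is why the two cases must be separated. It does not remove the conflict, because the same table has a separate row, with a 15% limit, for endpoint data not collected.

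**Zero total cost should be rare.** Entrants have had cancer treatment within 12 months (Section 5.3) and continue standard care (Section 6.8). Section 9.7 assumes test-arm averages of 3.45 ED visits and 1.8 planned outpatient visits. This also stands for total cost. Zeros could be more common for hospital costs, which the definition column names, but the documents give no figure for either.

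**Larger distortions.** Shares of 0%/20% would make the saving vanish, and 15%/5% would inflate it by 67%. Neither should be relied on. At mean 8,000, 20% zeros force an SD of exactly 4,000, with every billed participant at 10,000. At mean 10,000, 15% zeros force at least 4,201, above the plan's SD.

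**FACT-G.** A reader of the Protocol might infer that FACT-G data would be dropped for people with no bills. That is strained: FACT-G has its own ITT set, repeated-measures model and multiple imputation in Protocol Sections 9.1 and 9.2. The wording is a leftover.

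**Conclusion.** The concern holds as an internal conflict plus a missing rule. Section 11.1 of the Combined document describes removing no-bill participants from the primary analysis, Sections 9.1 and 9.2 require all randomized participants in a comparison of means, and nothing distinguishes a confirmed zero from absent claims.

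If the row is followed, the planned saving of 2,000 becomes anything from about 1,115 to 2,668 over the feasible shares shown. These sizes rest on the plan's means, on 4,000 being an SD, and on assumed no-bill shares. The direction is not fixed, so the documents do not support saying that the rule works for or against the programme. If zeros are rare, the bias is small.

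Severity is should-fix. The effect on a primary result applies to the Combined document; in the Protocol the same issue touches an exploratory comparison.

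**What to change.** **Combined protocol and SAP, Section 11.1.** Replace the row with one counting participants without claims access covering the analysis window. Treat only those participants as missing.

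**Combined protocol and SAP, Section 9.2.** State that a participant with confirmed access and no bills enters as zero. Restrict the GLM choice to a model that admits zeros and estimates the difference in overall means, for example a two-part model or a GLM whose family allows zeros.

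**Protocol.** Make the same row change in Section 11.1 and remove the stale reference to the primary objective analysis. Apply the same zero rule to the exploratory expenditure comparison. The rule can sit with that objective in Section 3, because Sections 9.2 and 9.3 of the Protocol contain no expenditure model.

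**Cost.** Wording in both documents, plus a check that each participant's claims access covers the window. Access is already scheduled in Section 6.1, but the documents do not say that its coverage of the window is recorded. Keeping the zeros leaves the planned saving at 2,000 and the sample size at 102 before drop-out and 146 after it.

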11.2 Data Quality Assurance

1. Electronic Data Capture:

- Since the trial is virtual with survivors located anywhere in the United States, and the intervention is delivered through a in-house custom HIPAA-compliant software product, we will have a custom form system directly in the same software for survivors to enter self reported data.

2. All Data stored is in AWS with appropriate data redundancy rules in place.

3. Data Validation: Data entered goes through testing (e.g. outliers, missing rows, etc) before being entered into the database.

4. Electronic Health Records and Claims Records: All medical data and billing data will be shared by survivors using their electronic access to their data i.e. medical records, claims data, and prescription drug costs.

- A clear PDF with instructions and screenshots will be shared for survivors to do this easily.

- We will recommend survivors give us access for a minimum of 6 months and a maximum of 18 months to minimize streamline survivor workload.

References

1. <https://www.ncbi.nlm.nih.gov/pmc/articles/PMC8576825/>
2. <https://www.ncbi.nlm.nih.gov/pmc/articles/PMC9454950/>
3. https://progressreport.cancer.gov/after/physical_activity
4. <https://www.cancerresearchuk.org/about-cancer/what-is-cancer/why-some-cancers-come-back>
5. <https://www.ncbi.nlm.nih.gov/pmc/articles/PMC7071977/>
6. https://journals.lww.com/acsm-msse/fulltext/2019/06000/physical_activity_in_cancer_prevention_and.20.aspx
7. <https://www.ncbi.nlm.nih.gov/pmc/articles/PMC6623989/>

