 - Motivation to work: Assessed through self-reported scales or questionnaires.
 - Performance review scores: Obtained from employer records or self-reported performance evaluations.
- Estimand(s): The difference in mean scores of motivation and performance reviews between the intervention and control groups over the trial period.

Exploratory Objective(s):

Impact on rates of cancer progression, and recurrence

Clinical Question: What is the effect of Complement Theory's program on progression and recurrence of prostate, lung and colorectal cancers?

- Endpoint(s):
 - Cancer progression: Measured by changes in tumor size and changes in levels of biomarkers.
 - Recurrence: Incidence of cancer recurrence.
- Estimand(s): Directional trends evaluating the difference in proportions or rates of cancer progression and recurrence between the intervention and control groups during and post-trial follow-up.

Rationale for Excluding Breast Cancer from Exploratory Objective:

- Breast cancer, in particular, exhibits a longer average timeframe for recurrence when compared to prostate, lung and colorectal cancers. This longer latency could extend beyond the scope of our study's follow-up period, making it

challenging to accurately measure the program's impact on recurrence rates within the study's duration.

- By focusing on prostate, lung and colorectal cancers, we aim to assess the program's impact on cancers with more predictable progression patterns and well-established biomarkers, enabling a clearer evaluation of the Complement Theory's potential benefits in these specific cancer populations.

Impact on Total Healthcare Expenditure

Clinical Question: Does participation in Complement Theory's 12-month Live coactive Coaching program, focusing on Exercise and Meditation and supplemented with evidence-based information on Diet, Sleep, and other lifestyle practices, adjunct to the core treatment, lead to a reduction in total healthcare expenditure for cancer survivors?

- Endpoint(s): Total healthcare expenditure, including hospitalization costs, medication expenses, outpatient visits, and any other related healthcare services that we planned and unplanned, cancer and non-cancer, over the trial period.
- Estimand(s): The difference in mean total healthcare expenditure between the intervention and control groups over a specified period (e.g., at 12 months and 18 months from baseline).

3.1 Summary of objectives, endpoints and estimands:

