5.3 Inclusion Criteria

- Cancer Type : Breast, Prostate, Colorectal, Lung and Other Cancers
 - Other Cancers here refers all other cancer types apart from Breast, Prostate, Colorectal and Lung Cancer
- Cancer Stage: Stage 1 to 4
- Treatment Status: Has undergone any cancer-related treatment in last 12 months
- Age : 21 to 64
- Permission to access to last 1 year digital health records
- Access to smartphone or a tablet

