6.1 Schedule of Events

Schedule of events for test/treatment group:

		Week	Week	Month 1-6	Month 7-18
Intervention or Assessment (Test)	Baseline (Day -30 to -1)	1/3/5/7/9/11/13/15/17/19/21/23	2/4/6/8/10/12/14/16/18/20/22/24	(Every 30 days)	(Every 30 days)

Live 1:1 Lifestyle Coaching - 3-5 days per week, 45 mins each		X	X		
Async access to Lifestyle modification content curated by CT		X	X		
Informed Consent	X				
Eligibility Criteria Assessment	X				
Demographic Details	X				
EHR Access Consent	X				
Claims Data Access	X		X		X
QoLS (FACT-G Form)	X		X		X
Weight	X		X		X
Physical Activity (GLTEQ)	X		X		X
Pain (BPI-ShortForm)	X	X	X		X
PROMIS (Short Form)	X	X			X
Adherence	X	X			X

(MMAS-8)					
Motivation to work	X	X			X
Employee Performance Review	X	X			X
Absenteeism Questions	X	X			X
Claim data validation with survivor				X	X
Cancer Progression Status				X	X

Schedule of events for active comparator (control) group:

Intervention or Assessment (Test)	Baseline (Day -30 to -1)	Week 1/3/5/7/9/11/13/15/17/19/21/23	Week 2/4/6/8/10/12/14/16/18/20/22/24	Month 1-6 (Every 30 days)	Month 7-18 (Every 30 days)
Async access to publically available lifestyle modification guidance		X	X		
Informed Consent	X				
Eligibility Criteria Assessment	X				
Demographic Details	X				
EHR Access Consent	X		X		X
Claims Data Access	X		X		X
QoLS (FACT-G Form)	X		X		X
Weight	X		X		X
Physical Activity	X		X		X

(GLTEQ)					
Pain (BPI-ShortForm)	X	X	X		X
PROMIS (Short Form)	X	X			X
Adherence (MMAS-8)	X	X			X
Motivation to work	X	X			X
Employee Performance Review	X	X			X
Absenteeism Questions	X	X			X
Claim data validation with survivor				X	X
Cancer Progression Status				X	X

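### The 6-month minimum for record and claims access in 11.2 is shorter than the 12- and 18-month expenditure windows, and no rule separates a month without access from a month without cost

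*Combined protocol and SAP*

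**What the plan says.** - **Access period.** Section 11.2 of the Combined protocol and SAP, on health and claims records: "We will recommend survivors give us access for a minimum of 6 months and a maximum of 18 months". The Protocol's 11.2 has the same sentence. Neither says when the period starts or whether it may include time before baseline.
- **Cost windows.** Section 9.2 of the Combined document bases its primary comparison on the "difference in mean total healthcare expenditure between the intervention and control groups at 3, 6, and 12 months and 18 months from baseline". In the Protocol, expenditure is exploratory, and Section 3 offers time points "at 12 months and 18 months from baseline" as examples.
- **Schedule.** Section 6.1 of both documents marks claims access at baseline, in even-numbered weeks, and every 30 days in months 7 to 18. A separate row, "Claim data validation with survivor", runs every 30 days from month 1 to month 18.
- **Look-back.** Section 5.3 makes this an entry criterion: "Permission to access to last 1 year digital health records". It names health records, not claims.
- **Missing expenditure data.** Section 9.2 of the Combined document makes complete cases the primary analysis. It then allows last observation carried forward (LOCF) for intermittent gaps and chained-equation multiple imputation (10 datasets) for more systematic gaps. Section 9 of the Protocol has no expenditure model and no missing-data rule for expenditure.
- **Other sources.** Participants also self-report expenditure (Section 8). Section 11.1 describes participants with no bills at all as censored.

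**The concern.** A cumulative cost total at 12 or 18 months can be built from claims only if claims are visible for the whole window. The plan schedules collection to month 18 but tells participants that 6 months of access is enough. A participant can therefore follow 11.2 exactly and still have no complete 12- or 18-month claims total.

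In the Combined document this is the primary endpoint, and its first analysis uses complete cases, so short access turns directly into lost sample. There is also a question of definition. A claims feed that ends at month 6 looks the same as a participant with no later bills. The plan sets no coverage requirement for a complete case and no rule for telling the two apart.

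**Working it through.** **1. The plan's own figure.** Inputs from 9.7 of the Combined document: means 10,000 and 8,000, spread 4,000, alpha 0.05 one-tailed, power 80%, 1:1 allocation, 51 per arm. The table calls 4,000 a variance. Read that way (SD 63.2), the formula gives 1 per arm. Read as an SD, it reproduces the plan:

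- Normal approximation: n = 2 × (1.645 + 0.842)² × (4,000 / 2,000)² = 49.5, so 50 per arm.
- One-sided t-test: 51 per arm, 102 in total, as stated.
- 102 / (1 − 0.30) = 145.7, so 146, as stated.
- Power at 51 per arm: 81% (0.811 by normal approximation, 0.806 by t-test).

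**2. Coverage of each window.** Coverage = months of access after baseline / months in the window, capped at 100%.

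| Access after baseline | 3 months | 6 months | 12 months | 18 months |
|---|---|---|---|---|
| 6 months (stated minimum) | 100% | 100% | 6/12 = 50% | 6/18 = 33% |
| 12 months | 100% | 100% | 100% | 12/18 = 67% |
| 18 months (stated maximum) | 100% | 100% | 100% | 100% |

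**3. Loss under the complete-case rule.** The share with full 18-month coverage is not in the documents, so a range is assumed. It is applied to the 51 per arm left after the 30% dropout allowance, because 9.7 ties that allowance to length of follow-up and not to access. The 9.7 row does not name its window; it is taken here as the 18-month total. The noncentrality is 2,000 / (4,000 × √(2/n)), with a one-sided 5% t-test.

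| Full coverage | n per arm | Noncentrality | Power (t) | Power (normal) |
|---|---|---|---|---|
| 100% | 51 | 2.52 | 81% | 81% |
| 75% | 38.25 | 2.19 | 70% | 71% |
| 50% | 25.5 | 1.79 | 55% | 56% |
| 25% | 12.75 | 1.26 | 34% | 35% |

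**4. What LOCF would do to a running total.** Suppose cost accrues evenly, access ends at month 6, and the month-6 total is carried to month 18. Months 7 to 18 then add nothing, and the recorded value is 33% of the true one.

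- Equal coverage in both arms shrinks the difference. If half of each arm has 6 months, mean coverage is 0.5 × 1 + 0.5 × 0.333 = 67%, and 2,000 becomes 1,333. With no true effect the difference stays at 0.
- Unequal coverage biases it in either direction. With no true effect and 10,000 in both arms, mean coverage of 90% in control and 80% in test gives an apparent saving of 9,000 − 8,000 = 1,000. The reverse gives −1,000.

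These coverage splits are illustrations, not forecasts.

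**The case against.** The strongest reply is that 11.2 is a recommendation about workload and not a cut-off for collection. Access for 18 months from baseline covers every window, 6.1 schedules claims to month 18 with monthly checks, and participants self-report expenditure too. Section 9.2 already treats missing expenditure data as missing, and 11.1 sets a 15% limit on participants without endpoint data.

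Much of this stands. Later windows are not incomplete for everyone, only for those who give less than the window needs. But Section 8 describes self-report as supplementing and validating claims and health records, and a monthly check of claims cannot supply claims that were never opened. The 15% limit prompts a review but does not define coverage.

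Two stronger readings are tempting and are not supported:

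- **That missing months count as savings for the program.** No section sets unobserved months to zero. Complete cases come first, LOCF is optional, and participants without bills are called censored. Equal under-coverage dilutes the difference. A false saving needs both zero-filling and lower coverage in the test arm, and nothing in the documents predicts that imbalance.
- **That full coverage needs 30 months (12 before and 18 after baseline), so that even the 18-month maximum fails.** The look-back in 5.3 is a separate entry permission for health records. Nothing says it uses up the period in 11.2. The silence should be resolved, but it does not show a shortfall.

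**Conclusion.** The point holds as an inconsistency between 11.2 and the 12- and 18-month cost comparisons, together with a gap in definition. The 50% and 33% coverage at the stated minimum follows from the documents, provided access runs forward from baseline.

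The fall in power to about 70%, 55% or 34% depends on the assumed share with full coverage, on 4,000 being an SD, on the 9.7 means applying at 18 months, and on short access being additional to dropout. If people with short access are largely those who would drop out anyway, the loss is smaller. Multiple imputation could recover part of it, but the primary analysis is stated as complete-case. The zero-cost effect is conditional: it arises only if LOCF is applied to a cumulative total, or if months without access are summed as months without bills.

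The weight is greatest in the Combined document, where expenditure is primary. In the Protocol it is exploratory and the FACT-G primary endpoint does not depend on claims, so the priority there is lower.

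**What to change.** In 11.2 of both documents, replace the 6-to-18-month recommendation with one period for everyone, from baseline through month 18, in line with 6.1. State that the one-year look-back permission in 5.3 is additional to it.

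In 9.2 of the Combined document, and in a short expenditure paragraph added to Section 9 of the Protocol:

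- record the months of claims access for each participant;
- define a complete case at each window as access for the whole window;
- treat a month without access as missing, and a month with access but no bills as zero cost;
- do not apply LOCF to cumulative cost;
- handle partial coverage by multiple imputation (already planned in the Combined document) or by an exposure term in the expenditure model.

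The cost is a wording change in 11.2 and Section 9, in the participant instruction PDF, and in the consent text where it covers access. The schedule does not change, because claims access through month 18 is already in 6.1. The downside is that a few participants may decline the longer permission. The change is best made before participants grant access, because months never opened may not be recoverable later.
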